### Table 2Intervals between study visits

D: Day; M: Month; PCR: Polymerase chain reaction; TC: Telephone call.

\* Visit 1 should take place no longer than 14 days after the Screening visit. All screening procedures, except the SARS-CoV-2 PCR test, need to be performed within 14 days of Visit 1 (see Section 8.1 and Section 8.3). A SARS-CoV-2 PCR test needs to be performed within 7 days of Visit 1. When applicable, a sample may be collected for repeat testing at any time (but only once to assess eligibility) before Visit 1. Only laboratory results from the repeat test, if it occurs, will be taken into consideration. The participant can only be assigned to a study intervention group once the investigator receives the results and confirms eligibility.

# 2. INTRODUCTION

# 2.1. Study rationale

As part of developing a novel mRNA vaccine platform, GSK selected the SARS-CoV-2 S glycoprotein as a model antigen (mRNA-CR vaccine). This is an exploratory, FTIH, observer-blind, randomized, controlled study, evaluating various doses of mRNA-CR-04 in individuals who have previously received:

• 2-dose primary series and booster dose(s) of an authorized or licensed mRNA COVID-19 vaccine (only Moderna or Pfizer vaccines) with the last booster dose administered at least 6 months or more prior to screening.

The safety, reactogenicity and immunogenicity of the mRNA-CR-04 vaccine administered in healthy adults previously vaccinated with a SARS-CoV-2 mRNA vaccine will be evaluated. The decision to move this mRNA construct and dose forward for the development of vaccines for a specific disease will be based on safety, reactogenicity, and immunogenicity profiles of the construct compared to the current standard of care.

# 2.2. Background

Due to the ongoing impact of COVID-19, there is a need for vaccines to provide protection against COVID-19 caused by SARS-CoV-2 variants of concern. As of 03 March 2023, more than 675 million cases have been reported worldwide, leading to more than 6.8 million deaths [Mathieu, 2023]. To date, there are multiple licensed or conditionally approved vaccines available that rely on a variety of vaccine technologies.

With the surge in Omicron predominance worldwide, its greater transmissibility, and a higher risk of SARS-CoV-2 reinfection with Omicron [Garcia-Beltran, 2021; Zhou, 2021], it is reasonable to anticipate an urgent need for booster vaccines to expand immunity against Omicron and additional future variants of concern. Bivalent boosters encoding Omicron BA.4/5 and the ancestral S protein sequences, followed by monovalent boosters encoding XBB.1.5 since 11 September 2023, have been authorized

for all doses administered to individuals 6 months of age and older [FDA, 2023a; FDA, 2023b].

Please refer to the current IB for information regarding preclinical studies of mRNA-CR-04 vaccine.

# 2.3. Benefit/risk assessment

Detailed information about the known and expected benefits and risks and expected AEs of mRNA-CR-04 vaccine can be found in the IB.

With any vaccine, administration site (e.g., pain, swelling, redness) and systemic (e.g., fever, fatigue, headache, myalgia) post-dosing events may occur within the first 3 days of study intervention administration, and are anticipated to be resolved within a few days of onset.

Syncope can occur following an injectable vaccine or even before any vaccination as a vasovagal response to the needle injection. Similarly, hypersensitivity reactions may also occur.

Currently, there are no identified preclinical risks for the investigational mRNA-CR-04 vaccine. However, the following important potential risks and mitigation strategies have been defined for this vaccine:

Important/potential/risk of clinical significance	Summary of data/rationale for risk	Mitigation strategy			
All study vaccines					
Hypersensitivity reactions including allergic reactions such as anaphylaxis	Acute allergic reactions such as a rare case of anaphylactic event may occur with any vaccine - administration. These are serious, but rare occurrences estimated in the range of 1 to 10 cases per million of vaccinations, depending on the vaccine studied [Rüggeberg, 2007].	A history of hypersensitivity or severe allergic reaction (including anaphylaxis) is an exclusion criterion for study participation and a contraindication to vaccination. The onset of vaccine-related allergic symptoms is typically quite prompt. To treat participants with a serious allergic vaccination reaction, all participants will need to remain under observation (i.e., visibly followed; no specific procedure) at the study site for at least 60 minutes after vaccination. Participants will be instructed to contact the study site immediately for occurrence of any possible hypersensitivity reaction within 1 day following study intervention administration.			
Bleeding following intramuscular injection	As with other intramuscular injections, study intervention should be given with caution in individuals with bleeding disorders, such as hemophilia or on anticoagulant	To minimize the risk of bleeding, study intervention should be given with caution in individuals with thrombocytopenia or any coagulation disorder.			

# **Risk Assessment**

Important/potential/risk of clinical significance	Summary of data/rationale for risk	Mitigation strategy
	therapy, to avoid the risk of hematoma following the injection.	Participants with any medical condition that in judgment of the investigator would make intramuscular injection unsafe will be excluded from study enrollment.
mRNA-CR-04 vaccine		
Myocarditis/pericarditis	Myocarditis/pericarditis are considered as an important identified risk for marketed mRNA COVID-19 vaccines [EMA, 2021a; EMA, 2021b; FDA, 2021a; FDA, 2021b] The estimated reporting rates of myocarditis in younger adults [25- to 29-year old] following the first and the second doses of BNT162b2 vaccine were 0.7 and 5.7 per 100 000, respectively and following the first and the second doses of mRNA-1273 vaccine were 1.8 and 11.2 per 100 000, respectively [CDC, 2021]. The same reporting trend was observed following booster mRNA vaccination, except for age, with most cases reported in older adults [ACIP, 2021].	Participants at increased risk of myocarditis/pericarditis or with medical history of myocarditis/pericarditis are excluded from study enrollment. Participants will also be instructed (via informed consent form) to be alert for symptoms of myocarditis/pericarditis and immediately contact the site if any of these symptoms occur. Participants will be tested for cardiac troponin I and undergo EKG at the screening and on D8 after study intervention administration. Participants will receive close medical supervision and medical assessments (e.g., laboratory testing) during the study. Moreover, myocarditis/pericarditis will be collected as an AESI and adjudicated (refer to Section 8.3.8,Section 8.4.4 and Section 10.3.5)
Vaccine-associated disease enhancement	Enhanced disease following vaccination has been observed in pre-clinical or clinical studies with various vaccines (e.g., RSV, Dengue, SARS) and the mechanism is poorly understood [Peeples, 2020]. While there are literature reports of enhanced disease in animals vaccinated with previous SARS vaccines, some other reports fail to see this effect.	During informed consent process, participants will be informed of this theoretical risk and asked to report any symptoms consistent with COVID-19 and/or for which they received medical attention at any point during the study. Any suspected, probable, or confirmed case of COVID-19 (regardless of severity) is an AESI; and will be captured and described (refer to Section 8.4.4 and Section 10.3.5)

AESI: Adverse event of special interest; EKG: Electrocardiogram; D: Day; RSV: Respiratory syncytial virus; SARS: Severe acute respiratory syndrome.

### Benefit assessment

Participants may gain information about their general health status through medical evaluations/assessments associated with this study (i.e., physical examinations and blood testing [hematology and biochemistry data]).

### **Overall Benefit: Risk conclusion**

The investigational mRNA-CR-04 vaccine is currently in an early stage of clinical development and vaccine efficacy, immunogenicity, and safety have not yet been demonstrated in humans.

Based on the available data for currently authorized/licensed mRNA COVID-19 vaccines, some potential risks have been defined. Appropriate safety monitoring and evaluation methodologies are in place to quickly identify any such events, should they occur.

Thus, while the benefit of this vaccine has not yet been proven, the anticipated potential risks for the mRNA-CR-04 vaccine are justified by the anticipated potential benefits.

# 3. OBJECTIVES, ENDPOINTS, AND ESTIMANDS

	Objective(s)	Endpoints/Estimands	
Primary			
•	To evaluate the safety and reactogenicity of investigational mRNA-CR-04 vaccine up to D31	
 
Solicited administration site events and systemic events during the 7-day follow-up period after study vaccine administration (day of study vaccine administration and 6 subsequent days);
 
Unsolicited AEs during the 30-day follow-up period after study vaccine administration (day of study vaccine administration (day of study vaccine administration and 29 subsequent days);
 
Any hematological and biochemical laboratory abnormality during the 15-day follow-up period after study vaccine administration (day of study vaccine administration and 14 subsequent days);
 
MAAEs; SAEs; AESIs* up to D31.
 
	
Secondary Safety			
•	To assess safety of investigational mRNA-CR-04 vaccine from study vaccine administration up to study conclusion.	
 
MAAEs; SAEs; AESIs* up to study conclusion (M6).
 
	
Secondary Immunogenicity			
•	To evaluate the Ab functionality (neutralizing capacity induced by the mRNA-CR-04 vaccine against vaccine encoded SARS-CoV-2 and WT strains) up to study conclusion.	
 
Neutralizing titer GMTs against pseudovirus bearing S protein from vaccine encoded SARS-CoV-2 and WT strains at each collection timepoint (D1, D15, D31, M6).
 
GMR from baseline (D1) of neutralizing titer against pseudovirus bearing S protein from vaccine encoded SARS-CoV-2 and WT strains at each collection timepoint.
 
Vaccine response rate based on neutralizing titers against vaccine encoded SARS-CoV-2 and WT strains at each collection timepoint.
 
	
Tertiary			
•	To describe serum-binding antibody (IgG) responses induced by the mRNA-CR-04 vaccine specific for vaccine encoded SARS-CoV-2 and WT strains S protein up to study conclusion.	
 
GMCs of binding IgG Ab specific for S protein encoded by the vaccine SARS-CoV-2 and WT strains at each timepoint (D1, D15, D31, M6).
 
GMR from baseline of binding IgG Ab specific for S protein encoded by the vaccine SARS-CoV-2 and WT strains S proteins at each timepoint.
 
Seroresponse rates based on binding IgG concentrations specific for S protein encoded by the vaccine SARS-CoV-2 and WT strains S protein at each timepoint.
 
	

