# 4. STUDY DESIGN

# 4.1. Overall design

**Experimental Design:** Phase 1, observer-blind, randomized, placebo-controlled, multicenter, dose-escalation study to evaluate in Part A of the study, 3 doses (10  $\mu$ g, 30  $\mu$ g, and 100  $\mu$ g) of the mRNA-CR-04 (Omicron BA.5 strain) vaccine (Figure 1) in 3 groups (Group 1, Group 2 and Group 3) (Table 4). Part B of the study will commence only after all Part A participants have completed their Day 15 study visits and the Day 15 interim analysis is completed. In Part B (Table 5), 2 doses (3  $\mu$ g and 10  $\mu$ g) of the mRNA-CR-04 (Omicron BA.5 strain) vaccine will be evaluated (Figure 1). The study will be conducted in the United States (US).

Duration of the study: Approximately 6 months after dosing.

**Sentinel dosing**: In Part A of the study, each group will have 8 sentinel participants (6 receiving the mRNA-CR-04 vaccine and 2 receiving a placebo) who will be enrolled and

vaccinated in each group. The first and second sentinel participant in each group will be vaccinated and followed-up for 24 hours before the next sentinel participant can be vaccinated. Vaccination of the remaining sentinel participants in the same group will then continue with an interval of at least 60 minutes between participants. Additionally, an interval of at least 60 minutes will be maintained between the vaccination of sentinel participants across groups.

**Dose-escalation:** In Part A of the study, enrollment of participants in Group 1 and Group 2 will be done in parallel with the first participant to be enrolled in Group 1. All safety data up to Day 8 post-vaccination from sentinel participants in both groups will be reviewed by the iSRC (unblinded review). The iSRC members will determine whether any of the pre-defined holding rules are met or if there is any other safety signal. If no safety signal is observed, vaccination of the non-sentinel participants in that group will continue. If no safety signal observed from sentinel participants in Group 1 and Group 2, enrollment and vaccination of the sentinel participants in Group 3 will be initiated. In Part B, irrespective of dose, all participants in the three study groups will be enrolled in parallel.

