2c*	Any Grade 3 unsolicited AE, that can be reasonably attributed to the vaccination as per investigator or sponsor assessment, with an event onset within the 7-day (Day 1-7) post-vaccination period OR Any Grade 3 or above abnormality in pre-specified hematological or biochemical laboratory parameters with an event onset within the 8- day (Day 1-8) post-vaccination period except for non-clinically significant leukopenia	≥2/6 or 10%***

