# Figure 2 Probability of not meeting holding rules 1 and 2 for 8 participants per study group

## 8.3.7.4. SRT and iSRC evaluation

The study will be overseen by an iSRC operating under a charter. Core members of the iSRC will include a GSK safety physician, a CSL and a biostatistician who are not otherwise involved in the conduct of the project. The iSRC safety reviews will be conducted using unblinded data. The iSRC will have access to the participant randomization and will review unblinded data.

In addition to the iSRC, the project SRT will review blinded data until the Part A Day 15 interim analysis, and unblinded data subsequently, on a regular basis throughout the study.

The iSRC will review accumulated unblinded safety data of the sentinel participants of each group up to 7 days post-vaccination. The iSRC will include all safety data sources in their Day 8 safety review (i.e., solicited safety data, unsolicited safety data, SAEs and AESIs, as well as laboratory safety data). If no pre-defined holding rule is met (refer to Section 8.3.7.3) or if no safety signal is observed the remaining participants in the group can be vaccinated and vaccination in the next group can be initiated.

In case the iSRC, through the in-stream data monitoring of all the accumulated safety data available detects that a holding rule is met, the study vaccination will be temporarily paused in all study groups and sites pending review of safety data by the iSRC. The iSRC will make relevant recommendations to the GSB chair(s), who will make the final decision whether vaccination can be safely resumed or not.

In addition, at any time during the study, if one of the holding rules 1a through 1d (refer to Table 12 for details) is met, the investigator will immediately inform the CRO team. Vaccination will be paused and an urgent ad-hoc meeting of the iSRC will be called to thoroughly review the event(s) and recommend to the GSB whether vaccination can be safely resumed or not. The GSB chair(s) will make the final decision whether vaccination can be safely resumed or not.

In Part B of the study, the iSRC will only be requested to review unblinded data if a study holding rule is met or if the SRT identifies a safety concern through in-stream data monitoring of unblinded data.

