## Statistical analysis methods

The number and percentage of participants reporting AEs up to 30 days after the dose (Day 31):

- At least one administration site event (solicited and unsolicited), with at least one systemic event (solicited and unsolicited) and with any AE (solicited and unsolicited) during the 7-day and 30-day follow-up period will be tabulated by treatment. Same tabulations will be performed for Grade 3 AEs (all and causally related) and for any causally related AEs.
- Each individual solicited administration site event (any grade and Grade 3) and solicited systemic event (any grade and Grade 3) during the 7-day follow-up period will be tabulated by maximum intensity per participant for each treatment group.
- Fever will be reported as number and percentage of participants reporting temperature per 0.5°C cumulative increments as from ≥38°C or 100.4°F during the 7-day follow-up period (i.e., on the day of study intervention administration and 6 subsequent days) and will be tabulated for each treatment group.
- At least one unsolicited AE during the 30-day follow-up period after the dose, as classified by the MedDRA SOC and PT will be tabulated by treatment group. The same tabulation will be performed for Grade 3, any causally related, Grade 3 causally related unsolicited AEs and unsolicited AEs with medically attended visits.
- For each treatment group and for each hematology and biochemistry parameter:
  - The number and percentage of participants having hematology and biochemistry results below or above the laboratory normal ranges will be tabulated by time point.
  - The maximum grading post-dose up to Day 15 will be tabulated versus baseline (Day 1, or if not available, closest visit available to D1 before IMP administration). Grades will be based on the FDA guidance for industry "Toxicity grading scale for healthy adults and adolescent volunteers enrolled in preventive vaccine clinical trials" (Section 10.2.2).
- At least one MAAE, SAE and AESIs after the dose, as classified by the MedDRA SOC and PT, will be tabulated by treatment group. The same tabulation will be performed for causally related MAAEs, SAEs and AESIs during this period. The detailed listings of SAEs, AESIs and COVID-19 cases will also be produced.

• At least one concomitant medication (any medication or any antipyretic) during the 7-day follow-up period and during the 30-day follow-up will be summarized by treatment group.

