Secondary	One dose of the investigational mRNA-CR vaccine.	Healthy adults, 18 to 49 years of age, who were primed and received booster dose(s) of an authorized or licensed mRNA COVID -19 vaccine with the last booster dose administered at least 6 months or more prior to	the 15-day follow-up period after study vaccine administration (day of study vaccine administration and 14 subsequent days); • MAAEs; SAEs; AESIs up to D31. MAAEs; SAEs; AESIs from Day 1 up to study conclusion (M6).	•	Study vaccination not administered as per protocol Any intercurrent conditions or any concomitant medication/vaccination that may confound the safety investigational product causality assessment prior to M6	The data collected from all participants receiving one dose of investigational vaccine will be used regardless of whether the intercurrent event occurs (Treatment policy) Rationale: treatment policy strategy is used as all data will contribute to evaluate the safety parameters	Proportion of participants in each treatment group for each endpoint

Estimand			Att	ribut	es		
	Treatment	Population	Endpoint (Variable)	ble) Intercurrent events (ICEs)		- Summent	
					Description	Handling strategy	Summary measure
		inclusive at the time of the vaccination.					
Secondary	One dose of the investigational mRNA-CR vaccine.	Healthy adults, 18 to 49 years of age, who were primed and received booster dose(s) of an authorized or licensed mRNA COVID -19 vaccine with the last booster dose administered at least 6 months or more prior to screening, inclusive at the time of the vaccination.	Neutralizing titer against pseudovirus bearing S protein from vaccine encoded SARS-CoV-2 and WT strains at each collection timepoint (D1, D15, D31, M6).	•	Study vaccination not administered as per protocol A condition that has the capability of altering the immune response (e.g., HIV, lymphoma, COVID) to the study intervention or is confirmed to have an alteration of the participant's initial immune status Major protocol deviations including out of visit window blood samples.	The Hypothetical strategy will be used. The data after the ICEs will be ignored. Rationale: To estimate the treatment effect on participants who are dosed and have no major protocol deviations.	Geometric Mean Titer for each treatment group

Estimand		Attributes							
	Treatment	Population	Endpoint (Variable)		Intercurrent ev	vents (ICEs)	Summani		
					Description	Handling strategy	Summary measure		

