Any hematological and biochemical laboratory abnormality during the 15-day follow-up period after study vaccine administration (day of study vaccine administration and 14 subsequent days);	
 
For each treatment group and for each Hematology and biochemistry parameter:
 
The number and percentage with exact 95% CI of participants having hematology and biochemistry results below, within, or above the laboratory normal ranges will be tabulated by time point.
 
The number and percentage of subjects reporting a grading increase from baseline at Day 8 and
 

Primary Safety Endpoints	Statistical Analysis Methods
	Day 15 separately. The maximum grading post
	vaccination up to Day 15 (i.e. Day 1 – Day 15) will
	be tabulated versus baseline. Grades will be
	based on the FDA guidance for industry "Toxicity
	grading scale for healthy adults and adolescent
	volunteers enrolled in preventive vaccine clinical
	trials" (Protocol Section 10.2.2).
	The listing of safety laboratory results will be
	provided
MAAEs; SAEs; AESIs up to D31.	The number and percentage with exact 95% CI of
	participants reporting MAAEs, SAEs, and AESIs after
	the dose up to Day 31 (i.e. with onset from Day 1 to Day
	30 post vaccination), as classified by the MedDRA SOC
	and PT, will be tabulated by treatment group. The same
	tabulation will be performed for causally related MAAEs,
	SAEs and AESIs during this period (i.e. with onset from
	Day 1 to Day 30 post vaccination).
	The detailed listings of SAEs, AESIs and COVID-19
	cases will also be produced.

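### Safety-laboratory periods stop before the permitted visit windows do, so compliant samples can miss the primary laboratory endpoint and the rule 2c count

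*Protocol*

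**What the plan says.** The primary laboratory endpoint in Protocol Section 3, Table 3, is "Any hematological and biochemical laboratory abnormality during the 15-day follow-up period after study vaccine administration (day of study vaccine administration and 14 subsequent days". Protocol 9.4.1 plans the matching shift table: "The maximum grading post-dose up to Day 15 will be tabulated versus baseline". SAP 4.2.1.1 writes the same period as a range, "vaccination up to Day 15 (i.e. Day 1 – Day 15) will", and places beside it a by-visit table: "The number and percentage of subjects reporting a grading increase from baseline at Day 8 and" Day 15.

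Protocol Table 12 limits the laboratory limb of holding rule 2c to "laboratory parameters with an event onset within the 8- day (Day 1-8) post-vaccination period". For the sentinel review, Protocol 4.1 says "All safety data up to Day 8 post-vaccination from sentinel participants in both groups will be reviewed by the iSRC", and Protocol 8.3.7.4 says "The iSRC will review accumulated unblinded safety data of the sentinel participants of each group up to 7 days post-vaccination".

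Protocol Table 2 allows Visit 2 at 7 to 9 days and Visit 3 at 12 to 16 days after Visit 1. According to the Schedule of Activities and Table 9, hematology and chemistry are drawn at screening, Visit 1 (before dosing), Visit 2 and Visit 3. SAP 6.2.1 counts the dosing day as Day 1.

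**The concern.** Both laboratory periods end on the planned visit day, not at the edge of the window in which the visit may take place. A participant seen late but within the window has done nothing wrong. Even so, the Visit 3 result can fall outside the primary endpoint and the Visit 2 result can fall outside rule 2c.

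For the analysis, a programmer who follows the stated range would drop a Day 16 or Day 17 sample from the maximum-grade table. The neighboring by-visit table would probably still count it under Day 15, so two tables in the same SAP section could disagree about one participant. This also sits badly with SAP Table 2. The primary estimand there uses a treatment-policy strategy on the ground that all data contribute. For immunogenicity blood from the same visit, the test is the visit window, with "Major protocol deviations including out of visit window blood samples" listed as an intercurrent event. A Day 17 titer would be kept while the Day 17 chemistry could be dropped.

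For the holding rule, the documents do not settle whether a Grade 3 or higher result from a permitted Visit 2 on Day 9 or 10 counts toward the trigger. The decision would then rest on iSRC judgment instead of the pre-specified count.

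**Working it through.** **Convention.** Study day = (assessment date − dosing date) + 1 (SAP 6.2.1). The endpoint's last day is 1 + 14 = Day 15.

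**Windows.** The Schedule of Activities gives 7 days (+2) for Visit 2 and 14 days (±2) for Visit 3. This reproduces Table 2's 7–9 and 12–16 days.

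| Visit | Days after dosing | Study days | Period ends | Permitted days outside |
|---|---|---|---|---|
| 2 | 7, 8, 9 | 8, 9, 10 | Day 8 (rule 2c laboratory limb) | 9, 10: 2 of 3 |
| 3 | 12 to 16 | 13 to 17 | Day 15 (endpoint, maximum grade) | 16, 17: 2 of 5 |

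Visit 2 has no early side, so only a visit on exactly Day 8 is inside the rule 2c period. These are counts of permitted days, not shares of visits. Both planned days are inside.

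**Visit 3 samples affected.** The documents give no distribution of actual visit days, so the late share q is an assumption. There are 18 vaccinees per group and five vaccine groups: 5 × 18 = 90.

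| q (Day 16–17) | Per group, 18q | All vaccinees, 90q |
|---|---|---|
| 0% | 0 | 0 |
| 5% | 0.9 | 4.5 |
| 20% | 3.6 | 18 |
| 40% | 7.2 | 36 |

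**Rule 2c as stated.** Protocol 8.3.7.3 gives about 90% probability of not holding at 9% true incidence, and 80% of holding above 42%, with 2 or more of 6. By exact binomial:

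- Not holding at 9%: 0.91⁶ + 6 × 0.09 × 0.91⁵ = 0.905.
- Holding at 42%: 1 − 0.58⁶ − 6 × 0.42 × 0.58⁵ = 0.797.

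Both agree with the protocol.

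**Rule 2c with late Visit 2 samples.** Assume that the threshold stays at 2, that onset is dated to the blood draw, and that Day 9–10 results are not counted. With m of the 6 sentinel samples on Day 8, the holding probability at 42% is 1 − 0.58^m − m × 0.42 × 0.58^(m−1):

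| m | 6 | 5 | 4 | 3 | 2 |
|---|---|---|---|---|---|
| P(hold) | 0.797 | 0.697 | 0.559 | 0.381 | 0.176 |

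A second view supposes that exactly two vaccinated sentinels have a Grade 3 or higher result at Visit 2, each late independently with probability q. The chance that the formal count stays below 2 is 1 − (1 − q)², which is 0%, 19%, 44% and 75% for q = 0%, 10%, 25% and 50%.

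**After the change.** With the endpoint period running to Day 17, 0 of 5 permitted Visit 3 days fall outside.

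**The case against.** The strongest reply is that Day 15 is a visit label. The Schedule of Activities heads Visit 3 that way with a ±2 window, and Protocol 4.1 speaks of Day 15 visits. Reading the Day 15 interim cut by calendar would drop in-window immunogenicity samples, which nobody intends. This reading is plausible elsewhere but does not fit Table 3, which counts the dosing day and 14 further days. It also fits poorly with SAP 4.2.1.1, which turns Day 31 into calendar onset days 1 to 30 for the adverse-event tables. No visit-assignment rule resolves the matter.

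It is also fair to say that nothing disappears from the database. The by-visit tables and the listing would probably show a late result, and the study is descriptive with no hypothesis tests. That limits the harm, but the gap still touches a primary endpoint.

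On rule 2c, the laboratory limb runs one day longer than the adverse-event limbs, which suggests that the Visit 2 sample was meant to be included. Onset might be judged earlier than the draw, although no dating rule is given. The iSRC looks for any other safety signal, and Protocol 8.3.7.2 escalates a signal in the same way as a met rule, so a late result need not go unseen. Meeting conduct is left to a charter that is not among these documents. The 2-of-6 trigger concerns Part A sentinels only, since Part B has none. All of this stands as mitigation. None of it says whether a permitted Day 9–10 result counts.

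**Conclusion.** The concern holds and should be fixed. On the documents' own day counts, 2 of 5 permitted Visit 3 days fall outside the primary laboratory endpoint and the maximum-grade table, and 2 of 3 permitted Visit 2 days fall outside the laboratory limb of rule 2c. Either wording of the iSRC sentinel review also stops short of Days 9 and 10.

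The day counts are exact. The number of participants affected is not known and could be zero, and every figure above that uses a late share is illustrative. The endpoint part rests on taking the stated calendar limits as written. The rule 2c part rests on dating a laboratory abnormality to its sample.

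**What to change.** - **Endpoint and maximum grade.** In Protocol Table 3, Protocol 9.4.1 and SAP 4.2.1.1, define both as all post-dose results through Visit 3 including its allowed window (study Day 17), excluding the pre-dose Day 1 sample.
- **Visit assignment.** Add one SAP sentence assigning scheduled laboratory results to nominal visits, so that the by-time-point, grade-increase and maximum-grade tables agree.
- **Holding rule.** The sponsor should reconcile Table 12 rule 2c, the review periods in Protocol 4.1 and 8.3.7.4, and the Visit 2 window in Table 2, so that it is explicit whether a laboratory result from a permitted Visit 2 counts. No particular rule is proposed here.

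The cost is wording only: no new samples, visits or participants. The protocol changes need an amendment and the ethics review that goes with it. The SAP sentence alone would align the tables but would leave Table 3 ending at Day 15.
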